13.0 Comparison of usual care and study procedures

If patients chose to not participate in this study, they will receive usual standard of care treatment for their cancer. This would include SLN mapping as per standard of care using technetium-99 +/- vital blue dye.

14.0 Withdrawal of Participants

Patients will be withdrawn from the study at their request. In addition, if their clinical situation evolves so that the SLN mapping is longer applicable to them or they no longer meet eligibility criteria, they will be withdrawn.

15.0 D

riorige	Theet engionity official, they will be withdrawn.
15.1 L	Management and Confidentiality Describe the steps the researchers will take to secure the data (e.g., training, authorization of access, password protection, encryption, physical controls, certificates of confidentiality, and separation of identifiers and data) during storage, use, and transmission. If HIPAA rules apply to the study, review information on the Office of Compliance HIPAA page and consult HIPAA Privacy and Security Coordinators to ensure that data management methods are compliant. Select all that apply: Data will be coded, and the "key" linking identities to codes will be kept separately from the data. Data will be coded, and the "key" linking identities to codes will be kept on paper only. The study data will be stored electronically and labeled only with codes. Only those listed as key personnel will have access to the "key." Access to the "key" will be limited to the following person (e.g., Database Administrator): This study is funded by the National Institutes of Health and is covered by a Certificate of Confidentiality. This study is NOT funded by the National Institutes of Health but because it will collect sensitive information, the research team will apply for a Certificate of Confidentiality to protect data from being requested without the subject's consent as part of a legal proceeding. Other: Other:
	Describe how and where data and/or specimens will be stored and maintained. Select all that apply: Online Collaborative Research Environment (OnCore) Biospecimen Management Research Electronic Data Capture (REDCap) Specify which instance you will be using (e.g., ICTR's, Department of Medicine's):

		Other software option that will be stored on departmental server. Specify the department:
		Locked filing cabinet or drawer inside a locked room. Specify the building: _Clinical Science Center (K6)
		Other (describe):
		Data will not be stored or accessed on portable devices.
	_	Portable devices will be used to access secure web-based data collection sites such as ICTR's REDCap. No data will be stored locally on the device.
		Data stored on portable devices will be coded with the key stored separately. No identifiers will be stored on portable devices.
		Data stored on portable devices and therefore only encrypted devices will be used.
15.4	Manage	ment of Identifiers:
		Identifiers will be destroyed after all data has been collected.
		Identifiers will be destroyed at study closure.
		Identifiers will be destroyed at study closure or at the time of publication.

15.5 Describe any planned sharing of data and/or specimens outside the study team / institution. Include sharing required by funding agencies and publications.

Imaging data will be coded with a unique sample ID # (e.g., 123) and will be stored on the secure surgery server and on the OnLume's off-campus data server. Data will be transferred using an encrypted USB drive. No PHI will be stored on the OnLume data server. The subject code is linked to a separate spreadsheet, which lists the subject number and the patient identifiable information including medical record number. The code will be stored separately from the research data on the secure Department of Surgery server. All electronic data is password and firewall security protected. When a patient is imaged through the Asimov Imaging Platform, only the subject ID will be entered into the system. In this way, the imaging will always be "coded" from the time of image acquisition. From the OnLume system, the imaging data will be transferred using an encyrpted USB hard drive. Once data is confirmed to be successfully transferred to OnLume and the secure Dept. of Surgery server, it will be permanently deleted from the imaging platform.

Datasets containing patient identifiers will not be copied or shared with others outside of the UW study team for analysis. Only datasets without identifiers can be shared for analysis; the Onlume team will only receive coded data. Upon completion of this research, the link to identifiable information will be destroyed, permanently de-identifying the data.

16.0 Provisions to Protect the Privacy Interests of Participants

16.1 Describe the steps that will be taken to protect participants' privacy interests. "Privacy interest" refers to a person's desire to place limits on with whom they interact or to whom they provide personal information. If any of the following apply, check the box for convenience:

Procedures will be performed in a private area where others cannot see the procedures being performed or overhear the conversation between subjects and researchers.

All members of the study team are up to date on their institutional HIPAA training.

The study is not collecting information that could pose legal or reputational risks to participants.

The consent process will occur at the Breast Center and pre-operative areas of UW Health. Subjects will be consented in a closed private room by a member of the study team. As much time as needed will be given for potential subjects to decide whether or not to participate in this study.

Patients being cared for by [name] within the UW Breast Center will be eligible for consideration. [name] will identify eligible patients from her clinical practice and introduce the study to them. A study team member will then discuss the study in detail and obtain informed consent. Once consent is obtained, a member of the research team with valid, approved access to HealthLink will conduct the chart abstraction from the health care record.

17.0 Sharing of Results

This is a feasibility study where patients' care will proceed using standard of care means. [name] will share with an individual patient the ICG-fluorescent imaging findings post-operatively at patients' request. Results will not be reported in the health record.

18.0 Data and Specimen Banking

We are not planning to retain data collected for future unrelated research projects.

19.0 Study Analysis

Baseline demographic and outcome variables will be summarized using descriptive statistics. We will report whether ICG-fluorescent lymph nodes were visualized percutaneously (prior to incision). We will describe concordance rates between technetium-99 and ICG-fluorescence for each sentinel lymph node removed (mean 2.8 nodes with a standard deviation of 2.2). We will also assess concordance at the patient level; using the technetium-99 as the gold standard,

we will describe the number of lymph nodes that would have been missed (i.e. technetium-99 + but ICG- in removed SLN) or would have been excised unnecessarily (i.e. residual ICG-fluorescence in axilla but no residual technetium-99) if ICG-fluorescent imaging had guided the SLN. We will summarize any adverse events.

Planned reporting of concordance rates between technetium-99 and ICG per excised sentinel lymph node						
Technetium-99 + Technetium-99 - Total						
ICG +						
ICG -						
Total						

20.2 Sample Size Justification:

No power calculation is calculated for this feasibility study. We anticipate that the sample size of 10 will be enough to assess initial feasibility of this approach and whether further study is warranted.

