Several potential challenges to using ICG for SLN mapping exist. First, challenges exist related to the devices used to detect ICG fluorescence. Many devices designed for ICG cannot optimally be used with ambient light, making it challenging to use to actively guide surgical dissection into the OR. In this proposal, we will determine the feasibility of using the Asimov Imaging Platform for fluorescence-guided surgery in the operating room. The Asimov can be used without altering external (i.e., room) light functionality or levels. In addition, it is mounted on an arm that can be positioned over the operative field. This facilitates real-time

visualization of lymphatics to support sentinel lymph node mapping during the dissection and would represent a significant advancement.

The second challenge relates to the penetration of the ICG imaging through skin and soft tissue. With the technetium, the option exists to obtain an image in radiology confirming the mapping was successful before coming to the OR; this allows for the potential for a second injection if needed for slow mapping. In the OR, a handheld probe is then used to localize the location of the lymph nodes in order to plan placement of the axillary incision. However, ICG fluorescence does not have the same depth of tissue penetration as technetium. In a recent clinical trial, the lymph nodes were not able to be visualized prior to skin incision using a hand-held fluorescence imaging device called Fluobeam 800. Consequently, the investigators planned their skin incision to be just lateral to the pectoralis muscle (where the majority of breast lymph nodes are located). Importantly. the ICG fluorescence was successful in identifying the sentinel lymph nodes once the skin incision was made. Given variation in device design, it is important to assess the feasibility of the Asimov Imaging Platform in identifying sentinel lymph nodes prior to and after skin incision.

The objective of this study is to assess the feasibility of using fluorescence-guided surgery with ICG dye through the Asimov Imaging Platform for the sentinel lymph node mapping. We will continue to use blue dye and technetium sulfur colloid to guide clinical decision making (standard of care).⁶ We will then compare the ICG fluorescence findings using the Asimov imaging Platform (research) with the blue dye and technetium sulfur colloid (standard of care).

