3.0 Study Objectives and Endpoints

Specific Aim 1: To determine the feasibility of using ICG fluorescence through the Asimov Imaging Platform for sentinel lymph node mapping by comparing lymphatic visualization using blue dye and technetium sulfur colloid (standard of care) versus ICG fluorescence imaging.

Specific Aim 2: To define optimal image acquisition parameters of using ICG fluorescence through the Asimov Imaging Platform for sentinel lymph node mapping to inform the clinical workflow.

- 2a. To define dynamic range of ICG fluorescence signal in lymph nodes and background tissue.
- 2b. To assess image contrast as a function of ICG dose and time post-injection.

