10.0 Study Intervention

Standard of Care Procedures:

SLN mapping using technetium-99m +/- isosulfan blue dye: For patients enrolled in the study, sentinel lymph node mapping and biopsy will be performed using technetium-99m sulfur colloid and isosulfan blue dye (unless there is a contraindication to blue dye); this is an acceptable standard of care. Injection of the technetium-99m sulfur colloid will be performed by the nuclear medicine team as per standard of care. The isosulfan blue dye injection will be performed by the participating surgeon in the operating room; as per standard of care, injection will be subareolar. Incisions will be planned based on the technetium-99m activity or at the lateral aspect of the pectoralis muscle, per usual care.

Research Procedures:

SLN mapping with ICG fluorescence using the Asimov Platform: The research procedures will include using ICG-fluorescent imaging for the SLN mapping. OnLume will provide a sterile drape designed specifically for the OnLume Asimov Platform. 25 mg of ICG and 10 mg Sterile Water will be dispensed for injection by UW Health pharmacy. Before the image acquisition of each patient, ICG will be reconstituted under sterile conditions with Sterile Water (2.5 mg/1 ml). The vial will be gently shaken to dissolve. Reconstituted ICG must be used within 6 hours after reconstitution. The total dose of dye will be kept below 2 mg/kg of patient body weight. The dose of ICG to be injected is based on the existing literature. 9,10 2 ml (5 mg) of ICG solution will be injected intradermally in 1-4 injection sites in the lateral areolar region. After injection, gentle manual massage will be performed for 5 minutes. ICG imaging will be obtained prior to incision. After incision is made (following standard of care procedures), the axilla will be visualized using the Asimov Platform to assess for ICG-fluorescence in sentinel lymph nodes.

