Impact on clinical care of the ICG mapping: The objective of this study is to evaluate the feasibility of using ICG fluorescent imaging through the Asimov Imaging Platform for SLN mapping. Compared to other platforms, the Asimov Imaging Platform allows real time imaging without altering ambient light. Clinical decisions regarding which lymph nodes are considered sentinel lymph nodes (and should be removed) will be made based technetium-99 activity and/or vital blue dye, as per standard of care. However, we will image with the Asimov Platform throughout to determine whether ICG-fluorescent imaging would have led to identification of different lymph nodes.

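### Section 19 counts a node as missed only against technetium, so a removed blue-only node that ICG does not show goes uncounted, although Aim 1 compares ICG with both tracers

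*Combined protocol and SAP*

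**What the plan says.** Specific Aim 1 (Section 3.0, repeated in Section 1.0) sets out to judge feasibility by "comparing lymphatic visualization using blue dye and technetium sulfur colloid (standard of care) versus ICG fluorescence imaging". The closing paragraph of Section 2.0 names the same two-tracer comparator.

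Under Section 10.0, decisions about which nodes are sentinel and should be removed are "made based technetium-99 activity and/or vital blue dye, as per standard of care". The same paragraph says that imaging runs throughout to learn whether ICG would have picked out other nodes. Blue dye is planned for each patient "unless there is a contraindication to blue dye"; Section 13.0 likewise treats it as optional within usual care.

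Section 12.0 records blue dye, technetium and ICG status for each removed node. Its check of the axilla after removal covers residual technetium and ICG, not blue dye.

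Section 19.0 takes the patient-level view "using the technetium-99 as the gold standard". It defines a missed node as "technetium-99 + but ICG- in removed SLN", and an unnecessarily excised node by residual ICG without residual technetium. Both describe what would have happened "if ICG-fluorescent imaging had guided the SLN". The table is headed "Planned reporting of concordance rates between technetium-99 and ICG per excised sentinel lymph node" and crosses technetium with ICG, with row and column totals. Section 19.0 does not name blue dye.

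**The concern.** The missed count is the plan's figure for what ICG guidance would have failed to find. As defined, it answers that question against technetium, whereas Aim 1 asks it against technetium and blue dye together. The two answers differ whenever standard of care removes a node on blue dye alone and ICG does not show it.

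The planned table does not make the difference visible. Such a node sits in the cell where technetium and ICG are both negative, which reads as concordance. A reader of the missed sentence could see zero missed nodes while that cell holds nodes that standard of care removed and ICG did not show. The study is meant to inform whether further work is warranted, and with only about 28 nodes expected, one or two uncounted nodes would visibly change the description.

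**Working it through.** **No stated figure to reproduce.** N = 10 is set without a power calculation, and no concordance target or blue-only share is given. The check therefore classifies nodes and illustrates the size.

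**Inputs.** 10 patients (Section 4.0). Mean 2.8 nodes, SD 2.2 (Section 19.0), read here as per patient. The blue-only share is not in the documents and is assumed below.

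**Classification.** Take every excised sentinel node to be technetium-positive (Tc+), blue-positive, or both, as the removal rule implies. Let m be the number that are Tc-negative, blue-positive and ICG-negative.

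- Planned missed count = number Tc+ and ICG-negative.
- Missed against standard of care = planned missed count + m.
- ICG detection among standard-of-care nodes = ICG-positive row total / all excised nodes.
- Overall Tc/ICG agreement = (both positive + both negative) / all excised nodes. Section 19.0 gives no formula for concordance; this is one natural reading.

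**Illustration.** Expected nodes = 10 x 2.8 = 28. Assume 26 Tc+ and 2 blue-only.

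| Tc+ nodes not shown by ICG | m | Planned missed | Missed vs standard of care | ICG detection | Tc/ICG agreement |
|---|---|---|---|---|---|
| 0 | 0 | 0 | 0 | 28/28 = 100.0% | 26/28 = 92.9% |
| 0 | 1 | 0 | 1 | 27/28 = 96.4% | 27/28 = 96.4% |
| 0 | 2 | 0 | 2 | 26/28 = 92.9% | 28/28 = 100.0% |
| 1 | 0 | 1 | 1 | 27/28 = 96.4% | 25/28 = 89.3% |
| 1 | 1 | 1 | 2 | 26/28 = 92.9% | 26/28 = 92.9% |
| 1 | 2 | 1 | 3 | 25/28 = 89.3% | 27/28 = 96.4% |

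The planned missed count does not move with m. Agreement, read as above, rises as ICG detects fewer blue-only nodes, while detection among standard-of-care nodes falls.

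**How likely is a shortfall?** Let p be the share of removed nodes that are blue-only and not shown by ICG. With n independent nodes, P(m ≥ 1) = 1 − (1 − p)^n. For n = 28 and assumed p of 1%, 3%, 5% and 10%, this gives 24.5%, 57.4%, 76.2% and 94.8%.

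Setting P(m ≥ 1) = 0.5 gives p = 1 − 0.5^(1/n):

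- n = 28: 2.4%
- n = 14: 4.8%
- n = 42: 1.6%

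The range 14 to 42 comes from the SD of the total, 2.2 x √10 = 6.96, and 28 ± 1.96 x 6.96 = 14.4 to 41.6 (normal approximation). Clustering of such nodes within patients would raise the break-even shares.

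**The case against.** Technetium is an explicit and defensible reference. It is the one standard tracer planned for every patient, it is the agent whose drawbacks motivate the study in Section 2.0, and Section 19.0 tells the reader that it is the gold standard. This stands, and nothing here asks for its removal. It does not answer the narrower point that the only missed rule for a two-tracer aim uses one tracer.

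A reader might infer that the blue-only nodes vanish from the report. The documents do not support that: the planned table includes both the technetium-negative/ICG-negative cell and the ICG-positive row total, so detection can be worked out if every excised sentinel node carried at least one standard tracer. Section 19.0 also promises descriptive summaries of outcome variables, which could cover blue status. What remains is that the table has no blue status and nothing interprets these counts against standard of care. Because blue dye can be withheld, a technetium-negative node in a patient without it could not be read as blue-only.

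A reader might also infer that the whole of Aim 1 rests on this count. It does not. Section 12.0 also collects visualization before incision, all three signals at each examination of the axilla, and lymphatic vessels seen by ICG or blue dye.

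Finally, the size is unknown. The break-even shares show when one uncounted node becomes likely, not that it will occur.

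**Conclusion.** The concern holds as a mismatch between the aim and the analysis rule. The missed count falls short of the standard-of-care count by exactly the number of removed blue-only nodes that ICG does not show. That this can happen follows directly from Sections 3.0, 10.0 and 19.0.

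Its size cannot be fixed from the documents and may be zero. The figures above rest on an assumed blue-only share, on 2.8 nodes being a per-patient mean, on independent nodes, and on every excised sentinel node carrying technetium or blue dye.

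The stronger conclusions that the technetium-by-ICG table is wrong, or that the feasibility conclusion would be invalid, are not supported. The table is correct for what its heading says, no success threshold or go/no-go rule uses the count, and ICG does not guide removal. The mismatch should be settled before results are known, but it is not a fatal flaw.

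**What to change.** In Section 19.0, keep technetium as gold standard, the technetium-by-ICG table and the existing missed count. Then add for Aim 1:

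- a count of removed nodes that are positive for technetium or blue dye and negative for ICG;
- ICG detection among nodes positive for either standard tracer, as a count and its denominator;
- the planned table split by blue status, from the per-node data in Section 12.0;
- patients given no blue dye shown separately, with technetium alone as their reference.

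The cost is one more table and a few sentences, with no new data or procedures. Three downsides should be stated in the report. The reference differs for patients without blue dye. The added figure is one-sided detection, not two-way concordance. The unnecessary-excision count stays on technetium alone, because the post-removal check in Section 12.0 does not record blue dye; the two halves of the what-if comparison would then use different references.

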20.0 Potential Benefits to Participants

There is no direct benefit to patient participation in this study.

21.0 Risks to Participants

There are low risks expected related to study participation.

Potential risks from ICG are minimal as it is a well-known, FDA-approved dye that has a very good safety profile (adverse event rate: 1 in 42,000) when administered intravenously. 11,19,20 Adverse events can range from a redness of the skin or hives, up to cough or difficulty swallowing. In the operating room, these would be treated with medication such as antihistamines, H2 blockers, and/or epinephrine. Although ICG is approved for intravenous administration, it has been safely injected into interstitial, subcutaneous (SC) or intradermal locations in hundreds of patients, including breast tissue. In a recent trial of 100 patients undergoing SLN with ICG-fluorescence, no ICG-related complications or adverse events were reported. In our own experience at UW using ICG for a lymphatic mapping study, no ICG-related complications have been experienced for the 6 patients enrolled to date. Similarly, no adverse reactions have been reported in other studies evaluating ICG for lymphatic mapping, with study sizes as large as 689 patients. 14-17,21

Potential risks from the use of the OnLume Asimov Imaging platform are low since the imaging device will be used in a similar manner as its FDA 510(k) clearance. The duration of the surgery is not expected to be significantly longer in

duration (<20 minutes) with the additional use of the OnLume System imaging than with just the standard of care. Per discussions with anesthesia staff, the additional time for anesthesia poses no foreseeable additional risk to the patient. The risk associated with the injection of the dye will be minimized by close observation of the patient after injection. Injection will occur in the OR when extensive monitoring is already occurring.

As with any study, there is a remote risk of breach of confidentiality. This risk has been minimized through data protection efforts. Only approved study personnel will have access to the direct identifiers.

22.0 Provisions to Monitor the Data to Ensure the Safety of Participants

The PI and study team will be involved in ongoing monitoring for data and safety concerns.

Our proposed phase II, non-blinded clinical trial represents a low risk of adverse events, and the described DSMP is commensurate with this level of risk. The PI and study team will meet weekly to discuss recruitment, accrual and retention of participants. They will also review any safety concerns during these meetings. The study team will discuss data quality monthly. The study team has developed a comprehensive checklist of study activities that resides within a regulatory binder. This will be reviewed before and after each patient is enrolled.

We feel that the risks to participating in this study are minimal and our research team will be continually reviewing data and subject safety at weekly study team meetings to discuss study progress including recruitment/enrollment, data integrity, and adverse events (AEs). This study will utilize the Common Terminology Criteria for Adverse Events (CTCAE) version 5.0 for routine toxicity and adverse event (AE) reporting. Incisional pain, breast seromas, and breast/arm swelling are expected events after breast and axillary surgery. We will consider injection site reactions, such as redness of the skin or hives, to be unexpected adverse events. We also consider allergic reactions to the dye (such as cough or difficulty swallowing) to be unexpected adverse events. We will submit any unanticipated adverse effects to sponsor and to the IRB as soon as possible, but no event later than 10 working days after the investigator first learns of the effect. Unexpected and immediately life-threatening or severely debilitating events, whether related to the ICG or the Asimov Imaging Platform, will be reported with 1 business day.

The focus of this study is to test the feasibility of ICG mapping through the Asimov Imaging Platform. Potential advantages to the Asimov Imaging Platform compared to other means of immunofluorescence detection is that it allows real time imaging without altering ambient light.

Only coded data related to the imaging acquisition will be stored on the OnLume off campus data server. Data will be transferred on an encrypted USB drive to OnLume. After confirmation that the data has transferred and is not been corrupted, the source data will be deleted from the imaging platform. Imaging data will also be stored on the surgery servers using the same method of encrypted USB. No PHI will be stored outside of the UW Department of Surgery secure server (see section that follows).

